2. METHODS

The study (Clinicaltrials.gov identifier NCT03594773) was conducted from July 2018 to March 2021 and enrolled patients at a large, urban, university-affiliated, mental health clinic. All study procedures were reviewed and approved by the Institutional Review Board of the University of Pittsburgh prior to the start of participant enrollment. Potential participants provided informed written consent after receiving a complete description of the study.

2.1 Study Design

This 10-week, randomized, parallel-group study enrolled adult participants with DSM-5-defined Major Depressive Disorder (MDD). We recruited study participants through University of Pittsburgh's online research registry and by advertisement. The study is divided into two phases because of disruptions caused by the COVID-19 pandemic. In Phase 1, psychotherapy was administered in-person.

Recruitment and study procedures were halted in March 2020. The study resumed in July 2020 as a completely remote study (Phase 2). In Phase 2, consent forms were sent to participants electronically and then reviewed by telephone. Psychotherapy was conducted over a secure video platform. This study is part of a larger project, Dyadic Behavior Informatics for Psychotherapy Process and Outcome (DAPPeR), in which data from this randomized controlled trial is used to model the dynamics of individual and dyadic behaviors on a moment-by-moment basis within each therapy session and over the course of treatment. Results from the DAPPeR project have been reported elsewhere (Vail et al., 2021; Vail et al., 2022).

2.2 Eligibility

Participants were adults who met the following criteria: (1) age 18-65; (2) DSM 5-defined (American Psychiatric Association, 2013) MDD, current episode (3) Hamilton Rating Scale for Depression-17 items (HRSD-17) (Hamilton, 1960) score ≥ 14 ; (5) if currently on antidepressant medication, on a stable dose for at least one month at the time of study entry and agreeable to remaining on that dose for study duration; (6) ability to read and speak English fluently, (5) capacity to give informed consent. For Phase 2 (telehealth therapy), the following inclusion criteria were added: (6) access to a computer with a camera and microphone; (7) access to headphones or earbuds that connect to device; (8) access to a private area to complete psychotherapy sessions without interruption; (9) access to broadband internet connection that meets the bandwidth criteria of minimum of 10Mb/sec for upload and download.

Participants were excluded from the study if they met any of the following criteria: (1) high risk for suicide, that, in the clinical opinion of the investigator, would warrant a higher level of care such as hospitalization or intensive outpatient programs; (2) current depressive episode has psychotic features; (3) current depressive episode has been present for > 104 weeks; (4) meets criteria for substance use disorders, as defined by DSM 5, in the past 3 months, except for caffeine or nicotine; (5) meets DSM 5 criteria for prior manic or hypomanic episode (bipolar I or II disorder) or a psychotic disorder including schizoaffective disorder or schizophrenia; (6) meets DSM 5 criteria for antisocial personality disorder; (7) significant, unstable, psychiatric co-morbidity that, in the opinion of the investigators, requires an alternative treatment approach (i.e., unstable eating disorder, unstable borderline personality disorder); (8) significant unstable medical illness that may explain depressive symptoms such as epilepsy, autoimmune disorder, chronic pain, or unstable endocrine disorder; (9) cognitive deficits that would preclude completion of study questionnaires or participation in psychotherapy; (10) unable or unwilling to comply with study requirements; (11) neurologic or medical condition that would interfere with nonverbal communication; at the discretion of the investigative team (e.g., severe visual impairment or facial paralysis).

Identifiers: NCT03594773 Unique Protocol ID: PRO17110528 Secondary IDs: 171722822

Title: Modeling Multi-level Dyadic Behavior to Transform the Science and Practice of Psychotherapy Process and Outcome. (DAPPeR)

Upload Date: December 8, 2023

Therapists were also research participants in this study and consented to participation. Inclusion criteria for therapist-participants were: (1) currently functioning as a therapist or supervisor for the Center for Advanced Psychotherapy (CAP) clinic; (2) capacity to give informed consent. There were no exclusion criteria for therapists.

2.3 Allocation

As shown in the CONSORT diagrams for Phase I and 2 (Figure 1), 638 potential participants during the Phase 1 study period and 149 during Phase 2 agreed to initial screening for inclusion in the protocol to yield 49 individuals eligible for randomization in Phase 1 and 28 in Phase 2. Participants were randomly allocated to either brief CBT (n=24 in phase 1; n=11 in phase 2) or brief IPT (n=25 in phase 1; n=17 in phase 2) by an independent data manager not otherwise involved in the clinical trial using a permuted block strategy (Matts and Lachin, 1988). The allocation sequence was concealed from all study personnel. Randomization was stratified by gender and depression screening scores, which accounts for imbalances in cell sizes.

2.4 Outcome Measures

Raters blind to treatment assignment conducted assessments in person (phase 1) or by telephone (phase 2) at baseline, midpoint (week 5), and post-treatment (week 10) except as indicated below. Self-report measures were collected online. Demographic data were recorded on standardized research forms. Psychiatric diagnoses were assigned using Mini-International Neuropsychiatric Interview (MINI version 7.0) (Sheehan et al., 1998). Information about antisocial personality disorder diagnosis was collected using the Structured Clinical Interview for DSM 5—Personality Disorders (SCID-5-PD) (First et al., 2016) Depressive symptoms were assessed using the clinician-rated HRSD-17 (primary outcome measure) and Montgomery Asberg Depression Rating Scale (MADRS) (Montgomery and Asberg, 1979), and the self-report Quick Inventory of Depressive Symptomatology-Self Report (QIDS-SR) (Rush et al., 2003). HRSD-17 scores range from 0 to 52, MADRS scores range from 0 to 60, and QIDS-SR scores range from 0-27, with higher scores indicating greater depression severity on all depression measures. QIDS scores were collected at each therapy visit. Anxiety was rated using the self-reported 7-item Generalized Anxiety Disorder Assessment (GAD-7) (Spitzer et al., 2006) with scores ranging from 0 to 21, with higher scores indicating greater anxiety severity. The self-reported World Health Organization Disability Assessment Schedule 2.0 (WHODAS 2.0), a 36-item measure with higher scores indicating more impairment, was used to assess global functioning (Federici et al., 2017). Acceptability of the intervention was assessed post-treatment with the Client Satisfaction Questionnaire (CSQ) (Attkisson and Greenfield, 1994) which yields scores ranging from 8-32 with higher scores indicating greater levels of satisfaction.

Both patients and therapists completed brief versions of the Working Alliance Inventory (WAI) (Horvath and Greenberg, 1989) after each therapy session. The therapist (10 items) and patient (12 items) versions of the WAI are designed to yield three alliance scales, corresponding to Bordin's components: Goal, Task, and Bond (Bordin, 1979). Higher scores indicate a more positive rating of working alliance. Both patients and therapists completed the 21-item Strategies in Therapy Use Form (STUF) after each therapy session. The STUF measure, developed for this study, is derived from patient and therapist self-report measures of the Psychotherapy Quality Questionnaire (PQQ) developed by Miranda and colleagues (Hepner et al., 2010; Miranda et al., 2010) to assess psychotherapy use in usual care settings. STUF measures therapeutic strategies used in sessions and is scored to yield IPT, CBT, and non-specific (NS) subscales. Higher scores on the STUF subscales indicate greater use of strategies related to the therapy modality. The CBT, IPT and NS scales showed a high degree of internal reliability across all 8 sessions for both the patient and therapist ratings (Cronbach alphas: .72 - .97; McDonald's Omegas: .70 - .97).

2.5 Interventions

Each participant was assigned an individual therapist who administered up to 8 sessions of psychotherapy weekly over a 10-week period, allowing for missed/rescheduled sessions. Each session

Identifiers: NCT03594773 Unique Protocol ID: PRO17110528 Secondary IDs: 171722822

Title: Modeling Multi-level Dyadic Behavior to Transform the Science and Practice of

Psychotherapy Process and Outcome. (DAPPeR)

Upload Date: December 8, 2023

lasted 50 minutes. In Phase 1, psychotherapy was administered in person; in Phase 2, psychotherapy was delivered over a HIPAA-compliant version of Zoom.

Brief IPT (IPT-B) addresses problematic interpersonal issues related to onset or maintenance of mood episodes (Weissman et al., 2018). IPT-B is designed to deliver a full course of IPT in 8 sessions, roughly half the length of “full dose” 16-session IPT (Swartz et al., 2004; Swartz et al., 2014). IPT-B offers the dual advantages of rapid relief from suffering and reduced practical barriers (time commitment) for overwhelmed populations (Swartz et al., 2014). In IPT-B, the therapist chooses one of three possible problem areas (grief, role disputes, or role transitions) to serve as the focus of treatment with the goal of selecting a relevant interpersonal issue that can be resolved in 8 sessions.

For *Brief CBT*, we adapted a CBT protocol designed to be administered over 4-8 sessions as an 8-session Brief CBT intervention (Cully and Teten, 2008). CBT focuses on modifying maladaptive thoughts and behaviors, using a combination of cognitive restructuring, behavioral activation, and problem solving and has a typical duration of 12-20 sessions (Beck et al., 1979). The first session consists of gathering additional information about current symptoms and goal setting. Each session began with setting an agenda and focusing on explicit goals, as well as eliciting feedback from the patient about the session. Patients were given homework assignments to practice skills between sessions. The relative focus on cognitive versus behavioral skills was adapted to the specific patient.

2.6 Statistical analysis

Analyses were conducted using SPSS28 and HLM8 (SSI, Inc.) statistical software. To compare groups by treatment and phase on baseline demographic and clinical characteristics, and treatment dropout rates and number of sessions completed, Cramer's V and Mann-Whitney Wilcoxon tests were used to compare nominal and ordinal variables, respectively. Independent samples t-tests were used to compare groups by treatment and phase on overall client satisfaction (CSQ). Analyses of outcome and process variables were conducted using hierarchical linear models (HLM, also known as linear mixed effects models) with weekly measures nested within persons (patients) and modeled with random slopes and intercepts, an unstructured variance/covariance matrix, and robust standard errors. HLM allows for inclusion of all subjects with at least baseline data and addresses missing data by using restricted maximum likelihood (REML) estimation. Time was centered at 10 weeks, and variables used for randomization stratification (gender and HRSD-17 screening scores) were included as covariates in all HLM models. Cohen's d-type effect sizes (absolute values) were calculated from model estimates for HLM models and from raw values for simple t-tests.

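### The CSQ treatment comparison omits the two randomisation stratifiers; it loses power only to the extent that they predict satisfaction, which the documents do not state

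*Combined protocol and SAP*

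**What the plan says.** Section 2.3 (Allocation) describes permuted blocks and states: "Randomization was stratified by gender and depression screening scores". The randomised numbers are "brief CBT (n=24 in phase 1; n=11 in phase 2) or brief IPT (n=25 in phase 1; n=17 in phase 2".

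Section 2.4 (Outcome Measures) gives the timing of the satisfaction score: "Acceptability of the intervention was assessed post-treatment with the Client Satisfaction Questionnaire (CSQ". It is measured once and has no baseline value. HRSD-17 is the primary outcome.

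Section 2.6 (Statistical analysis) treats the two kinds of outcome differently. For the mixed models, "variables used for randomization stratification (gender and HRSD-17 screening scores) were included as covariates in all HLM models". For satisfaction, "Independent samples t-tests were used to compare groups by treatment and phase on overall client satisfaction (CSQ". Effect sizes follow the same split: "effect sizes (absolute values) were calculated from model estimates for HLM models and from raw values for simple t-tests". No adjusted CSQ analysis is described.

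**The concern.** Stratified allocation balances the arms on gender and screening score, so the treatment difference varies less from one randomisation to another than it would under simple randomisation. An unadjusted t-test gives no credit for this. Its standard error still contains whatever part of the CSQ variance the two stratifiers explain. If they are prognostic, the interval is wider than it needs to be, the true size falls below the nominal 5%, and a real difference in acceptability is more easily missed.

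CSQ does not fit a repeated-measures model because it is measured once. That explains why it is outside the HLM, but it does not explain dropping the covariates, since an ordinary linear model can carry them. The precision of the CBT-IPT satisfaction comparison is at stake. The primary outcome is not.

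**Working it through.** The documents give no alpha, power calculation or CSQ result, so there is no stated figure to reproduce.

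**Inputs from the documents (section 2.3).** CBT 24 + 11 = 35; IPT 25 + 17 = 42; total 77. Stratifiers: gender and depression screening score. Permuted blocks.

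**Assumptions, not in the documents.** Two-sided 5% test; all 77 have a CSQ score; true standardised difference d = 0.5 for power; share of CSQ variance explained by the stratifiers (R²) from 0 to 15%; block size and number of strata varied as below.

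**Step 1: precision of the planned t-test, overall comparison.**
- SE(d) = √(1/35 + 1/42) = 0.229.
- 95% CI half-width = 1.992 × 0.229 = 0.456 SD.
- Noncentral-t power at d = 0.5: 57.8%.

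**Step 2: true size under perfect balance on the stratifiers.** The difference has variance proportional to 1 − R², but the t-test uses the full variance. Size = 2 × (1 − Φ(1.96/√(1 − R²))).

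| R² | True size |
|---|---|
| 0 | 0.050 |
| 2% | 0.048 |
| 5% | 0.044 |
| 10% | 0.039 |
| 15% | 0.034 |

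Omitting the stratifiers therefore lowers the size or leaves it unchanged.

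**Step 3: simulation with imperfect balance.** There were 77 patients and 10,000 runs per setting. Twelve allocation schemes were used: 4 or 8 strata (gender assumed 35/65, by 2 or 4 score bands); blocks of 4, 6 or 8; sequence continued or restarted in Phase 2. The t-test was compared with a regression on treatment, phase, gender and screening score. Ranges are over the 12 schemes.

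| R² | t-test size | Regression size | SE ratio, adjusted/unadjusted | Power at d = 0.5, t-test | Power at d = 0.5, regression |
|---|---|---|---|---|---|
| 0 | 0.047-0.054 | 0.047-0.054 | 1.004-1.009 | about 58% | 0.1-0.9 points lower |
| 5% | 0.043-0.049 | 0.047-0.053 | 0.979-0.983 | 57.8-59.2% | 59.2-60.2% |
| 15% | 0.033-0.041 | 0.047-0.053 | 0.926-0.930 | 57.7-58.9% | 63.7-64.8% |

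The gain within a scheme is 1.0-1.9 points at R² 5% and 5.6-6.2 points at R² 15%. A separate single-scheme run with blocks of 4 fills in the low end. Power was 57.8% against 57.9% at R² 1%, and 58.3% against 58.4% at R² 2%, t-test first. Those differences are within simulation error.

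**Step 4: effect on the interval.** The half-width of 0.456 SD becomes 0.456 × 0.98 = 0.447 at R² 5% and 0.456 × 0.928 = 0.423 at R² 15%.

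**Step 5: sensitivity to missing CSQ.** With an assumed 25% missing at random, t-test power at d = 0.5 falls to about 46%. The adjusted SE is then no smaller than the unadjusted one at R² up to 2%.

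**Step 6: cost of adding phase.** Treatment-phase correlation = (24×17 − 25×11)/√(49×28×35×42) = 133/1420 = 0.094. Variance inflation = 1/(1 − 0.094²) = 1.009, which is negligible.

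**The case against.** The best defence is that nothing here is contradictory. The covariate sentence in section 2.6 is confined to HLM models, CSQ is a single score outside them, and a t-test is simple and transparent. All of that stands. A reader might infer that the plan breaks its own rule or that the t-test is anti-conservative. The text supports neither: the rule does not reach CSQ, and ignoring stratifiers after stratified blocking pushes the size down.

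The second objection is that the loss depends on an R² that the documents do not give. This also stands. It rules out saying flatly that the test is slightly conservative: the loss may be nil.

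The third is that missing scores may matter more. CSQ is collected only after treatment, and section 2.6 itself compares dropout. With 25% missing, power falls by about 12 points (58% to 46%), which is more than adjustment recovers anywhere in the range shown. This stands as a limit on what the fix achieves. It is not a reason to leave out the covariates.

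The fourth is timing. The document describes a completed study in the past tense, so a changed test is post hoc. That is a reason to keep the t-test result visible and to say when the adjusted analysis was added. The choice of covariates is not open to suspicion, because the stratification fixed them in advance.

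**Conclusion.** The concern holds as a minor, inexpensive gain in efficiency. The CSQ treatment comparison leaves out two stratifiers that the trial collected and uses in every HLM model. The loss at d = 0.5 ranges from nothing material at R² 0-2%, through about 2 power points at 5%, to about 6 points at 15%. These figures assume all 77 have a score and a two-sided 5% test, and precision is lower with dropout. R², block size and strata definitions are assumptions.

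Two stronger readings should be resisted. First, that the t-test is valid without qualification and cannot show a false difference. The finding is only that omitting the stratifiers does not inflate the error rate. Differential return of CSQ could bias the comparison. If therapists worked in one arm only, which the documents do not state, clustering could raise the error rate. With an assumed 5 therapists per arm and R² 5%, the simulated t-test size was 0.066 at an intraclass correlation of 0.02 and 0.091 at 0.05. The stratifier regression does not cure this.

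Second, that the documents make a causal claim about telehealth from the phase comparison. They do not. A phase contrast is non-randomised: period and delivery mode changed together, and section 2.2 notes "For Phase 2 (telehealth therapy), the following inclusion criteria were added". Section 2.6 also leaves open whether treatment was compared overall or within phase. That is missing detail, separate from this point, and the figures above are for the overall comparison.

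**What to change.** Make the treatment comparison of CSQ a linear regression of observed CSQ on treatment, gender and HRSD-17 screening score. This puts CSQ on the covariate basis stated for the HLM models. Phase may be added at negligible cost in precision, but its coefficient should be labelled as a non-randomised comparison. Report the signed adjusted CBT-IPT difference with its 95% CI in place of an absolute effect size alone. Keep the t-test as a sensitivity analysis, and state that the adjusted analysis was added after the original one.

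The work is one regression on data already collected. If the stratifiers do not predict CSQ, the adjusted SE is 0.4-0.9% wider with full data and power at d = 0.5 falls by 0.1-0.9 points (both from the simulation that included phase). The change does not address missing CSQ or possible therapist clustering, which would need their own handling.

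### The CBT–IPT comparisons have no therapist term although therapists were very probably shared; report therapist caseloads and a therapist-adjusted sensitivity analysis

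*Combined protocol and SAP*

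**What the plan says.** **Model.** Section 2.6 describes a two-level model for outcome and process variables: "weekly measures nested within persons (patients) and modeled with random slopes and intercepts, an unstructured variance/covariance matrix, and robust standard errors". The covariates are gender and the HRSD-17 screening score. The time variable is coded so that the treatment difference is read at the end of treatment: "Time was centered at 10 weeks". Satisfaction is handled separately: "Independent samples t-tests were used to compare groups by treatment and phase on overall client satisfaction (CSQ"). No therapist random effect, fixed effect or therapist-clustered standard error appears anywhere.

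**Therapists.** Section 2.5 states: "Each participant was assigned an individual therapist who administered up to 8 sessions of psychotherapy weekly over a 10-week period". The therapist criteria at the end of section 2.2 require a person "currently functioning as a therapist or supervisor for the Center for Advanced Psychotherapy (CAP) clinic". Section 2 says that the study "enrolled patients at a large, urban, university-affiliated, mental health clinic".

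**Numbers.** Section 2.3 allocates patients to "brief CBT (n=24 in phase 1; n=11 in phase 2) or brief IPT (n=25 in phase 1; n=17 in phase 2").

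**Not given.** The documents do not state the number of therapists, their caseloads, how patients were matched to therapists, whether a therapist delivered one treatment or both, or any intraclass correlation (ICC).

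**The concern.** Both treatments are delivered by therapists. If some therapists obtain better results than others, patients of the same therapist have correlated outcomes. The planned analysis treats all patients as independent. The robust standard errors do not change this, because the highest unit in the described model is the patient.

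The consequence depends on how therapists were distributed over the arms. If each worked in one arm only, differences between therapists enter the CBT–IPT difference, and its intervals are too narrow. If each treated patients in both arms in balance, therapist differences largely cancel. The documents do not allow a reader to tell which case applies, and so how far to trust the reported intervals.

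**Working it through.** **Inputs from the documents.** CBT 24 + 11 = 35; IPT 25 + 17 = 42; total 77, which agrees with 49 + 28 in section 2.3. There is no power calculation, significance level or ICC to reproduce.

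**Assumed inputs.** Number of therapists in total K = 6, 12 or 24, near-equal caseloads, two-sided 5% level, and the therapist variances given below. The simulations leave out the stratification covariates and missing data.

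**Step 1. Is sharing likely?** Avoiding it would need 77 different therapists from one clinic. Sharing is therefore a strong inference, but still an inference.

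**Step 2. CSQ, therapists nested in arm.** With caseloads m and total variance 1, the true variance of the difference in means is

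V = ICC × (Σm²/35² + Σm²/42²) + (1 − ICC) × (1/35 + 1/42).

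For K = 6 the caseloads are 12, 12, 11 and 14, 14, 14, so the sums of squares are 409 and 588. At ICC 0.05:

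- V = 0.05 × (409/1225 + 588/1764) + 0.95 × 0.05238 = 0.0334 + 0.0498 = 0.0831.
- The pooled variance that the t-test expects is [0.05 × (35 − 409/35) + 0.95 × 34 + 0.05 × (42 − 588/42) + 0.95 × 41]/75 = 0.984, so it reports 0.984 × 0.05238 = 0.0516.
- True over reported standard error = √(0.0831/0.0516) = 1.27.
- Type I error = 2 × [1 − Φ(1.96/1.27)] = 12.3%.

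The same formula, with simulation (40,000 replicates) beside it:

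| K | ICC | SE ratio | Type I, formula | Type I, simulated |
|---|---|---|---|---|
| 6 | 0.05 / 0.10 | 1.27 / 1.50 | 12.3% / 19.1% | 12.2% / 18.8% |
| 12 | 0.05 / 0.10 | 1.13 / 1.25 | 8.3% / 11.7% | 8.3% / 11.3% |
| 24 | 0.05 / 0.10 | 1.06 / 1.11 | 6.3% / 7.7% | 6.2% / 7.7% |

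**Step 3. HRSD-17, therapists nested in arm.** Here the therapist is assumed to act only on change after baseline. Assumed variances: baseline 0.6, slope over 10 weeks 0.36, residual 0.5, with visits at weeks 0, 5 and 10.

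- Person-level variance at week 10 = 0.6 + 0.36 + 0.5 × (1/3 + 25/50) = 1.377.
- A therapist share of 5% / 10% of slope variance is an effective ICC of 0.018/1.377 = 0.013 and 0.036/1.377 = 0.026.
- At K = 12, true over reported standard error = √[1 + (77/12 − 1) × ICC] = 1.03 and 1.07.

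Simulated type I error of the planned robust test on t(75), 40,000 replicates:

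| K | share 0 | share 5% | share 10% |
|---|---|---|---|
| 6 | 5.2% | 7.1% | 9.2% |
| 12 | 5.2% | 6.0% | 7.2% |
| 24 | 5.2% | 5.6% | 5.9% |

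**Step 4. Is CSQ inherently worse affected than HRSD-17?** Steps 2 and 3 use different ICCs. In a separate run, the therapist share was 0.05 of the variance in both the true week-10 level and the single score. With 3, 5 and 8 therapists per arm, the robust week-10 test ran at 11.3%, 8.5% and 6.9%, against 12.4%, 9.0% and 7.5% for the t-test. Most of the contrast disappears.

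**Step 5. Therapists crossed with arm in balance.** HRSD-17 runs at 4.9–5.4% and CSQ at 4.1–4.6%. If therapists also differ in how well they deliver each treatment, with interaction variance equal to the therapist variance, HRSD-17 runs at 6.0% / 6.7% (K = 6), 5.6% / 5.8% (K = 12) and 5.3% / 5.4% (K = 24). CSQ at K = 6 runs at 7.8% / 10.7% for ICC 0.05 / 0.10.

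**Step 6. Which degrees of freedom in an adjusted analysis?** HRSD-17, nested, therapist slope coded from baseline, REML, 2,400 replicates (Monte Carlo error about 0.4–0.5 points), share 5% / 10%:

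| K | Planned test | Adjusted, t(K−2) | Adjusted, t(75) |
|---|---|---|---|
| 6 | 7.1% / 9.2% | 0.7% / 1.1% | 5.0% / 5.8% |
| 12 | 6.0% / 7.2% | 2.7% / 2.8% | 4.4% / 4.7% |
| 24 | 5.6% / 5.9% | 3.8% / 3.5% | 4.6% / 4.2% |

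The K−2 test is further from 5% than the planned test in four of the six cells, equally far in one and closer in one.

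**The case against.** **No error is shown.** The documents do not say that therapists worked in one arm only, and under balanced crossing the planned tests are adequate. This stands: a reader might infer that the standard errors are too small as reported, but the documents support that only conditionally. It does not remove the point, because the missing caseload information is what prevents a reader from deciding.

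**The effect on the primary outcome is small.** HRSD-17 is rated blind ("Raters blind to treatment assignment conducted assessments in person (phase 1) or by telephone (phase 2) at baseline, midpoint (week 5")), and with 12 or more therapists its test stays between 5.6% and 7.2% even when nested. The highest rates need three therapists per arm, and nothing in the documents indicates so few. This stands under the assumed variances.

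**CSQ looks worse only by assumption.** A reader might infer from the tables that satisfaction is much more exposed than HRSD-17. That therapists can act only after baseline is a fair reason to expect some difference, but its size comes mostly from the assumed ICCs (step 4).

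**Therapist-rated WAI and STUF.** A reader might infer that these are affected most, since one therapist may score several patients. That is plausible, but the documents give no ICC for them and no figure was computed.

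**The text is a past-tense methods section**, and caseloads may be reported with results not seen here. If so, the first part of the fix is already met.

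**Conclusion.** The omission of a therapist term is certain, sharing of therapists is very probable, and an error in the standard errors is possible but not established. If therapists were nested in arm with a non-zero therapist effect, the standard errors are too small. A nominal 5% test then runs at about 6–9% for HRSD-17 and about 6–19% for CSQ over 6 to 24 therapists, under the shares and ICCs assumed in steps 2 and 3. If therapists were crossed in balance without therapist-by-treatment variation, nothing material is wrong. With no therapist effect, or one patient per therapist, nothing changes.

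This is therefore an inexpensive improvement that should be made, not a demonstrated mistake in the plan. Nor does it justify replacing the planned analysis by one on K−2 degrees of freedom: step 6 shows that choice to be clearly conservative with few therapists.

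**What to change.** 1. **Report** the number of therapists and their caseloads by arm and phase, including whether any therapist delivered both treatments.
2. **Add a therapist-adjusted sensitivity analysis** beside the planned results.
   - For outcomes with a baseline (HRSD-17, MADRS, QIDS-SR, GAD-7, WHODAS 2.0), let the therapist act on change: a therapist random slope coded from week 0, or a therapist random intercept on post-baseline scores adjusted for baseline. A lone therapist slope on the plan's week-10-centred time is zero where the treatment difference is read. At K = 12, share 10%, on t(75), it left the test at 6.7% (planned 7.1% in the same replicates), against 4.7% with the slope coded from baseline.
   - For WAI, STUF and CSQ, use a therapist random intercept.
   - If therapists delivered both treatments, use a crossed therapist effect, with a therapist-by-treatment term where it can be estimated.
3. **Show both** patient-based and therapist-based (K−2) degrees of freedom. Do not rely on K−2 alone.

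**Cost.** No new data, provided therapist identity is in the dataset. That is likely, since therapists consented as participants and completed forms after each session, but it is not stated. If nested, HRSD-17 intervals on t(K−2) are wider by 44% / 52% at K = 6, 16% / 19% at K = 12 and 8% / 8% at K = 24 (share 5% / 10%). At K = 12 about 12% of this is only the change of reference distribution (2.228/1.992 = 1.12). CSQ intervals at K = 12 are 23% / 35% wider at ICC 0.05 / 0.10. The therapist variance will be imprecise: at K = 12 it was estimated at zero in 47% / 40% of simulated HRSD-17 trials. If crossed in balance, HRSD-17 intervals change by less than 1% and CSQ intervals narrow by 1–4%.

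### Does the primary HRSD-17, rated only at weeks 0, 5 and 10, need a categorical-visit model beside the random-slope HLM?

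*Combined protocol and SAP*

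**What the plan says.** Section 2.4 names the clinician-rated HRSD-17 as the primary outcome. It places assessments "at baseline, midpoint (week 5), and post-treatment (week 10) except as indicated below", and no exception is listed for the HRSD-17. The denser schedule belongs to other instruments: "QIDS scores were collected at each therapy visit", and the alliance and strategy forms are completed after each session.

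Section 2.6 then gives one model description for outcome and process variables together: "weekly measures nested within persons (patients) and modeled with random slopes and intercepts", with an unstructured covariance matrix, robust standard errors, REML, and the two stratification variables as covariates. Client satisfaction is the exception and has t-tests. On time, the section says only "Time was centered at 10 weeks". On effect sizes it says "Cohen's d-type effect sizes (absolute values) were calculated from model estimates for HLM models". It does not state whether time enters linearly, or whether the reported result is the week-10 arm difference or the arm-by-time slope.

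**The concern.** Three things invite the worry. The word weekly does not fit an outcome rated three times. A random slope with centred time suggests a straight line, yet depression scores in psychotherapy trials may fall faster early than late. And centring at week 10 makes the arm coefficient the week-10 difference, so that is a natural number to report.

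If the arm difference is not linear in time, that coefficient is not the week-10 difference alone. It mixes in the week-5 gap and could overstate or understate the end-of-treatment contrast on the primary outcome. A model with visit as a category and a 3x3 unstructured covariance would estimate week 10 directly from data already collected, so the improvement looks almost free.

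**Working it through.** **Inputs from the documents.** Visits at 0, 5 and 10 weeks (section 2.4). Arm sizes (section 2.3): CBT 24 + 11 = 35, IPT 25 + 17 = 42. The plan gives no SD, correlation, effect size or loss rate, so there is no design figure to reproduce.

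**Assumptions.** Linear time. Equal baseline means. SDs of 4/5.5/6.5 or 6.5 at every visit. Five correlation sets for visit pairs (0-5, 0-10, 5-10): (.4, .3, .5), (.5, .4, .65), (.6, .45, .75), all .3, all .5. That makes ten settings. Week-10 loss is independent of outcome. Stratification covariates are left out.

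**Weights.** With complete data, generalised least squares equals ordinary least squares under a random intercept and slope. Times have mean 5 and sum of squares 25 + 0 + 25 = 50. The fitted week-10 value puts weight 1/3 + (10 - 5)(t - 5)/50 on the visit at time t, which gives -1/6, 1/3, 5/6. The slope weight is (t - 5)/50, which gives -0.1, 0, +0.1.

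**Bias.** With true arm differences d5 and d10 and none at baseline, the week-10 term estimates d5/3 + 5 d10/6. Its bias is (2 d5 - d10)/6. The slope gives week 5 no weight, so it has no such bias with complete data.

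| Pattern | d5 | d10 | Week-10 bias, complete data | Week-10 bias, 20% lost after week 5 in both arms | Bias of 10 x slope, same loss |
|---|---|---|---|---|---|
| Grows to week 8, then flat | 3 x 5/8 = 1.875 | 3 | (3.75 - 3)/6 = +0.125 | +0.16 to +0.19 | +0.04 to +0.08 |
| Late | 0.75 | 3 | (1.5 - 3)/6 = -0.25 | -0.31 to -0.37 | -0.07 to -0.15 |
| All present by week 5 | 3 | 3 | (6 - 3)/6 = +0.50 | +0.62 to +0.74 | +0.15 to +0.29 |

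The first row is the most plausible: a patient attending weekly finishes 8 sessions by about week 8. Curvature shared by both arms cancels with complete data. With 10% versus 30% loss on a shared curve (20, 14, 11.5), the bias is 0.17 to 0.30 for the week-10 term.

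**Standard errors.** Categorical, SD 6.5: 6.5 x sqrt(1/35 + 1/42) = 1.49. For the linear model with equal SDs and a common correlation r, the variance is multiplied by 30/36 + (6/36) r. At r = .5 the factor is 0.917, so the SE is 1.49 x 0.957 = 1.42. Over the ten settings the linear SE is 1.38 to 1.53, and the categorical/linear ratio is 0.972 to 1.080. With 20% loss the linear SE is 1.47 to 1.61, the categorical 1.57 to 1.64, and the ratio 0.97 to 1.11.

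**Bias and precision together.** In the plausible row at r = .5 with complete data, the linear root-mean-square error is sqrt(1.42^2 + 0.125^2) = 1.43, against 1.49 for the categorical model. Over the ten settings, linear is equal or better in 7 with complete data and in 7 with 20% loss. The categorical/linear ratio runs from about 0.97 to 1.10. In the late pattern with 20% loss, linear is better in 6 of 10. Among these patterns the categorical model is better in most settings (8 of 10) only when the whole difference is already present at week 5.

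**Loss does not always add to the bias.** Put the plausible difference on IPT with the curve (20, 14, 11.5). Loss of 10% in CBT and 30% in IPT moves the bias from +0.125 to between -0.09 and +0.01. Reversing the loss gives +0.31 to +0.46.

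**The case for a change.** The best case for adding the model is that it needs one run per scale and no new data, it is feasible with 77 patients (six covariance parameters instead of four), and it removes dependence on a time shape that the text never states. Some patterns hurt more than the table shows: an early 3-point gap that has vanished by week 10 gives a linear estimate of (2 x 3 - 0)/6 = 1.0 when the truth is 0. The slope is not a complete refuge either, since it loses full protection once patients are lost after week 5.

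All of that is arithmetically right. What stands is that the reader needs to know the form of time and which term lies behind the reported effect size, and that weekly is loose wording for the HRSD-17. What does not stand is the step to a needed analysis. Nothing in the documents points to a vanishing early gap or to unequal loss. Linear time is itself an inference. The added model would have to settle how baseline enters, because a screening HRSD-17 is already a covariate and the text does not say whether it is the same measurement as week 0. And the study ran from July 2018 to March 2021, so the result would be a second, post hoc estimate of the primary outcome.

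**Conclusion.** No change to the plan. A random-intercept, random-slope model with REML, robust standard errors and the stratification covariates is a standard analysis of three visits, and following it has not been shown to give a wrong answer. The alternative is a trade-off: it removes a bias of about 0.1 standard error in the plausible pattern, while its standard error ranges from about 3% narrower to 11% wider. Reasonable statisticians would differ on that exchange, and in most of the plausible settings examined it does not improve accuracy.

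The word weekly is a clerical looseness, because the same paragraph also covers measures taken at every session. The form of time and the reported term are missing details that the results report would ordinarily supply; only a methods text is available here. Anyone wishing to run the categorical model can do so as an optional sensitivity analysis labelled post hoc, with the HLM remaining the governing analysis.

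The conclusion rests on linear time, equal baselines, loss unrelated to outcome, and the assumed SDs and correlations. Strong evidence of an early difference that later disappears, or of markedly unequal loss, would strengthen the case for the sensitivity analysis. The documents contain neither.
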